The researchers will deliver the Intervention with the patients participating in the study at leaving points, during the patient's journey through the COPD service, as specified in the diagram below. Patients enter the pulmonary rehabilitation (PR) section of the COPD service post-acute episode or by GP referral. Patients are then clinically assessed for suitability to continue in the exercise component of the service. If patients are deemed suitable for exercise then they continue onto PR. Post PR they have a review, 30 minutes with a clinician to ascertain their progress through the programme and to recommend continuation of exercise. At this point patients can also leave the programme.

Furthermore patients are offered maintenance exercise therapy – and are reviewed yearly, during these reviews other exercise and activity can also be recommended, patients can also leave the service at this point. These transition points in the care pathway; leaving the PR programme, or at

yearly maintenance review patients will be offered to participate in the GENIE study and provided with study information.

1. Those patients completing a PR programme, and in whom we wish to provide clear direction and signposting to appropriate social activity
2. Those who have benefitted from maintenance for 1 year or more, but at review could be encouraged to do more and have more social outlets.

Currently, patients leaving PR classes are usually offered the option to join the maintenance exercise class, delivered by the COPD team, other exercise options are considered, however, these options are currently limited or difficult to access in one place.

Building capacity to carry out the evaluation: Ensuring the GENIE database contains an appropriate library of social and health activities suitable for the Southampton COPD patient. The lead researcher will investigate existing exercise, social and community activities, then populate and categorise the GENIE database.

Introducing the intervention: In order to successfully implement the GENIE tool into clinical practice; the clinical team needs to be at the core of the process in order to ensure appropriate and effective facilitation. Therefore, the clinical team will be briefed as the study progresses, through question and answer sessions and direct learning opportunities in how the tool works and the objectives of the study.

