Selection and patient information: Patients in the COPD service; at the outset of their assessment, the end of PR and during maintenance sessions will be informed that the GENIE implementation evaluation is in progress.

Patients participating in these aspects of the service will be offered the opportunity to volunteer for the study, by the clinical team. If patients are interested they can then provide their names to the clinical staff to keep on a secure Solent database. Patient information sheets and invitation letters will be given out to the interested patients at their clinical visits to minimise postal and /or extra visits.

Once patients have received an information sheet, they will be allowed at least 72 hours to read and digest the information, (patient information sheets, consent and GP letters are separate documents), and share this with their friends and family if they wish to. Ideally, patients are provided with information in their clinical visits and are returning for clinical visits then appointments for research could be amalgamated with usual clinical visits. In this way extra study visits can be reduced. Patients, now participants, will be invited to consent and be randomised at the point of leaving usual clinical care. Furthermore, all patients at this point will have the opportunity to opt out of the study.

Once the participant is randomised (using block randomisation technique in clinic), then they will all receive normal clinical care (discharge planning with suggested activities), and the GENIE tool intervention, in the GENIE group, this is in addition to usual clinical care. Baseline questionnaires will also be administered at this visit.

The follow up period will commence 3 months (12 weeks) (+/- 1 week) from the day the GENIE tool was initially delivered. Participants will be invited back, via letter and /or phone call to attend their three month follow up visit at Bitterne Health Centre.

Solent NHS Trust will be the overall NHS organisation with one venue for study delivery; Bitterne Health Centre.

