Block randomisation technique, a commonly used technique in clinical trial design to reduce bias and achieve balance in the allocation of participants to treatment arms, especially in this case when the sample size is small (Efird, J. 2010). In order to reduce unconscious bias of the researcher, pre-prepared envelopes containing the possible combinations of group allocation, will be stored in a locked drawer in Bitterne Health Centre. The intention is to randomize in blocks of four, as this will complement the clinic structure. Therefore, each envelope will contain a pre-determined allocation pattern for that clinic (AABB, ABAB, BABA etc.).

The researcher team will share an excel spread sheet which will be set to generate a random number sequence. The next sequential number will be selected, which will then correspond to an envelope with the predetermined sequence. In this way the envelope selection is random, then sequence in the envelopes is also random, but ensures 50/50 grouping of participants. Baseline data for descriptive statistics will also be collected. (Data capture form appended)

In order to conduct meaningful analysis recruitment needs to reach at least 30 patients, in each group, however the maximum could be 60 in each group, 120 patients in total. Therefore recruitment could take between 6-9 months. The timeframe can be increased if necessary.

Initial / Baseline data collection:

Socio-economic data will be collected including; disease severity (FEV1), gender, EQ-5D, health care utilisation questionnaire, HEIQ and wellbeing questionnaires (CAT, GAD, PHQ-9), as well as an optional health behaviour questionnaire, from both the usual care group and the interventional group. Please note CAT, GAD, PHQ-9 FEV1 and gender are already captured routinely during clinical consultation.

Intervention

[figure not shown]
Assessment stratification and feedback:

Stage 1: The patient will complete a questionnaire online with the researcher/clinician. The patients will be asked to name the important people and activities in their network, type of relationship and frequency of contact using the concentric circles diagram.

Stage 2: The online process: consisting of series of questions will be used to elicit the participant's values and preferences for activities and support resources.

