Following the training, the participants will be given the tools required to roll out the intervention

- Paper and web-based concentric circles with typologies and support suggestions
- Guidebook on how to deliver GENIE
- Access to the database and website

Identification, enrolment and randomisation

[figure not shown]

Table of Events

	Consent and Randomisation	Pre – intervention data collection	12 weeks post intervention data collection (+/- 1 week)	Potential 1 year follow up phase
Consent form discussion and taking informed consent	x			
Randomisation (Block)	x			
EQ-5D		X	x	x
Health Care Utilisation Questionnaire		X	x	x
Socio-economic background / demographic data		X		
Gender		X		
Disease severity (FEV1)		X		
HEIQ (Self-management)		X	x	
Optional Health behaviour questionnaire		x	x	x
CAT		X	x	x
Gad-7 /		X	x	
PHQ-9		x	x	x
Uptake discussion / online survey			x	x

Quality Assurance

The delivery of the intervention will be taped in as many cases as consented to ensure that the intervention is delivered consistently by the research team to all patients. The tape recording is for quality assurance, and is not intended for research utilisation or publication.

Future work

The participants included in this initial 3 months of the study could be followed up again in 1 year (12 months) to ascertain longer term outcomes and longevity of connections made. This element could consist of a paper or online survey to understand the uptake rates of the social actives 1 year on, and further investigation into QOL, **healthcare use and the option of assessing health behaviours.** All participants would be given the option of continuing for a year, and therefore those who continue would be decided by participant preference to remain in the study.

Analysis Plan

Primary Outcomes

Descriptive statistics of the cohort,

Descriptive statistics of the cohort will be reported including but not limited to; age, gender, severity of disease then the analysis will be broken down into 5 distinct sections;

- a) Pre and post intervention cost utility analysis for the usual care group and the intervention group.
- b) Comparative group - pre and post cost utility analysis; calculated cost per QALY (quality adjusted life years) gained and cost of healthcare usage per patient– usual care group at 3 months after leaving the COPD service compared with the post intervention group 3 (+/- 1 week) months after leaving the COPD service, with significance.

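### The readable text lists randomisation before the baseline questionnaires and never requires baseline to be finished before the arm is known, leaving some self-reported baselines open to influence

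*Combined protocol and SAP*

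**What the plan says.** Under *Implementation Design*, the paragraph on selection and patient information gives the visit in this order. First: "Patients, now participants, will be invited to consent and be randomised at the point of leaving usual clinical care". Next: "Once the participant is randomised (using block randomisation technique in clinic), then they will all receive normal clinical care", with GENIE added in the intervention arm. Last: "Baseline questionnaires will also be administered at this visit".

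The *Table of Events* puts consent and randomisation in its first column. All seven self-report instruments have their baseline entry in the second, headed "Pre – intervention data collection".

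On allocation, the protocol gives its purpose: "In order to reduce unconscious bias of the researcher, pre-prepared envelopes containing the possible combinations of group allocation" are kept in a locked drawer. It goes on: "The intention is to randomize in blocks of four, as this will complement the clinic structure". And: "Therefore, each envelope will contain a pre-determined allocation pattern for that clinic (AABB, ABAB, BABA etc". A shared spreadsheet generates random numbers, and the next number identifies the envelope to use.

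On delivery: "The researchers will deliver the Intervention with the patients participating in the study". No blinding and no separate assessor are described.

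The paragraph on initial and baseline data notes that CAT, GAD, PHQ-9, FEV1 and gender are already recorded in routine consultations. It does not say whether those routine values are the trial baseline, or when they are taken relative to randomisation.

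**The concern.** A baseline is protected by randomisation only if it is fixed before anyone involved in reporting or recording it knows the arm. Here the person answering may know whether they are to receive GENIE, and the researcher beside them may be about to deliver it. Either can colour a self-reported answer. If that happens in one arm more than the other, the baseline carries a difference that randomisation did not create, and any analysis that subtracts, adjusts for or integrates from baseline inherits it.

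The pattern envelopes add to this. Once one is opened for a clinic, the researcher can know the arms of later participants in that block before their questionnaires are taken. That works against the purpose the protocol gives for the envelopes.

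**Working it through.** The protocol states no figure on this point, so there is none to reproduce. The check is of order, exposure and consequence.

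**1. Order.** The narrative runs consent, randomisation, care by arm, baseline questionnaires at the same visit. The table runs consent and randomisation, then pre-intervention data. Together they place baseline before GENIE. Neither says that the arm is still unknown when the questionnaires are completed.

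**2. Instruments.** Seven self-report instruments are scheduled at baseline.

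| Instrument | Routine clinic value named? | Exposure |
|---|---|---|
| EQ-5D, HEIQ, optional health behaviour | No | Clearest |
| Health care utilisation (3-month counts) | No | Less, because it asks for counts |
| CAT, GAD-7, PHQ-9 | Yes | Only if a routine value recorded before randomisation is not the baseline |

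**3. Participants.** Recruitment of 60 to 120 gives 60/4 = 15 to 120/4 = 30 blocks. If a pattern is opened before any baseline in the clinic, up to 4 of 4 baselines are exposed. If it is opened after the first baseline and the same researcher takes the rest, up to 3 of 4 are exposed, that is 3 × 15 = 45 to 3 × 30 = 90 participants. These are ceilings; the actual number cannot be known from the text.

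**4. Analyses.**

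| Analysis | Uses an exposed baseline? |
|---|---|
| *Analysis Plan* a), pre/post cost utility | Yes |
| b), cost per QALY | If baseline EQ-5D enters |
| b), healthcare cost at 3 months | No, if unadjusted |
| c), pre/post CAT and psychological impact | Only if routine pre-randomisation values are not the baseline |
| d), between groups at 3 months | No, if unadjusted |
| *Analysis of Outcomes*: between-group comparison at baseline; HEIQ and health behaviours, baseline to 3 months | Yes |
| *Secondary objectives*: change in health behaviours between groups | Yes |

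**5. Illustration of the mechanism.** Nothing in this step comes from the documents except the group sizes. Assume normal scores, no true effect, a shift of b SD in one arm's baseline, a fraction p of it persisting at 3 months, baseline-to-3-month correlation r, and a two-sided 5% t-test on between-arm change. The plan names no such test.

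- SE of the difference in change, in SD units: √[2(1 − r)] × √(2/n)
- Standardised bias: d = b(1 − p)/SE
- False-positive rate ≈ 1 − Φ(1.96 − d) + Φ(−1.96 − d)

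For n = 30 per arm, r = 0.6, b = 0.2, p = 0: SE = 0.894 × 0.258 = 0.231; d = 0.2/0.231 = 0.866; rate ≈ 0.137 + 0.002 = 0.139. Simulation (20,000 runs) gives 0.137. Simulated rates for r = 0.6 to 0.7:

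| n per arm | b = 0.1, p = 0 | b = 0.2, p = 0 | b = 0.2, p = 0.5 |
|---|---|---|---|
| 15 (health behaviour, if its 30 participants split equally) | 6% | 9–11% | 6% |
| 30 | 7–8% | 14–16% | 7–8% |
| 60 | 9–11% | 23–29% | 9–11% |

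If the whole shift persists (p = 1), the rate is 5%. An unadjusted 3-month comparison stays at 5% under a baseline-only shift. A baseline-adjusted one does not: 9–12% with 30 per arm and 13–18% with 60, for b = 0.2. The results follow the assumed shift: with b = 0.3 and r = 0.7 the formula gives 32% at 30 per arm and 56% at 60.

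**6. QALYs.** The plan does not say how they are computed. With a two-point trapezoid over 12 weeks, T = 12/52.18 = 0.230 years, and baseline utility carries weight T/2 = 0.115. An assumed shift of 0.02 to 0.05 in one arm's baseline moves the unadjusted QALY difference by 0.115 × 0.02 = 0.0023 to 0.115 × 0.05 = 0.0058.

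**The case against.** The strongest objection is that this is a claim of absence beside a missing figure. The section on identification, enrolment and randomisation consists of a figure that is not shown, and that is a likely place for the order of consent, baseline and randomisation. This stands, and it confines the point to the readable text.

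A reader might infer that the protocol directs baseline to be taken after the arm is disclosed. It does not. Saying that the questionnaires are also given at the visit is not a sequence, and sharing a column between consent and randomisation does not prove that the arm is announced first. The order is left open.

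A reader might also infer that all seven instruments and the main group comparison are compromised. Routine capture may protect CAT, GAD-7 and PHQ-9, and d) and the 3-month cost comparison use no baseline as written. Analyses a) and c), being within-arm, could not isolate an effect of GENIE even with a clean baseline.

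The error rates in the working rest on assumed shifts and on tests that the plan does not name. They show that the mechanism can matter, and they must not be quoted as this trial's error rates.

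Finally, 3-month self-reports are given by people who know their arm whatever is done at baseline, and an equal utility shift there would move QALYs by the same amount. That is true, but it does not justify leaving an avoidable weakness at baseline.

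**Conclusion.** The concern holds in a limited form. Following the readable text as written permits baselines taken with the arm known, and foreknowledge within a clinic block. The exposure is clearest for EQ-5D, HEIQ and health behaviour. It reaches the pre/post analyses, the baseline and change comparisons, and cost per QALY if baseline EQ-5D enters. It does not reach the unadjusted 3-month comparison d) or the 3-month cost comparison.

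The size and direction of any bias are unknown. The conclusion rests on the enrolment figure not already fixing the order, and on researchers or participants learning the arm when the envelope is opened. The change should be made because it is cheap and because an influenced baseline cannot be repaired afterwards. Confidence is medium, chiefly because of the missing figure.

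**What to change.** 1. In the paragraph on selection and patient information, state that after consent the participant completes every baseline questionnaire, and that only then is the allocation opened, followed by usual care with or without GENIE. Reorder the *Table of Events* to Consent | Baseline | Randomisation, and make both agree with the enrolment figure.

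2. If routine CAT, GAD-7 or PHQ-9 values serve as baseline, say so and require that they predate randomisation.

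3. In the randomisation paragraphs, replace the pattern envelopes with one sealed, opaque, sequentially numbered envelope per participant. Prepare these in advance from a randomly ordered list of blocks of four, and open them in strict number order after that participant's baseline. Use the spreadsheet's random numbers only to order the blocks when the list is prepared. Picking single-allocation envelopes by random number in clinic would break the blocks.

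The cost is wording edits and the preparation of 60 to 120 envelopes. No extra visits, staff or participants are needed, and nobody waits for another participant's questionnaires.

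One limit remains. With fixed blocks of four and known boundaries, some allocations can be deduced from earlier ones. Among the six patterns, AABB and BBAA each give away two and the other four give away one: 2 × 2 + 4 × 1 = 8 of 24, or one third. Varying the block size would reduce this, but it is optional because the protocol chose fours to fit its clinics.

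### One envelope holds a clinic's whole four-patient allocation pattern, so opening it can reveal up to three later allocations; the text also suggests that randomisation precedes the baseline questionnaires

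*Combined protocol and SAP*

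**What the plan says.** All references are to the combined protocol and SAP.

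- **Content of the envelope.** Under Selection and patient information, allocation is in blocks of four to suit the way clinics run, and "each envelope will contain a pre-determined allocation pattern for that clinic (AABB, ABAB, BABA etc".
- **Purpose and safeguard.** The plan gives the reason itself: "In order to reduce unconscious bias of the researcher, pre-prepared envelopes containing the possible combinations of group allocation" are to be kept in a locked drawer at the health centre.
- **Choice of envelope.** "The researcher team will share an excel spread sheet which will be set to generate a random number sequence". The next number on that list picks the envelope, and with it the whole sequence.
- **Who treats.** Under Implementation Design: "The researchers will deliver the Intervention with the patients participating in the study at leaving points".
- **Timing of randomisation.** "Patients, now participants, will be invited to consent and be randomised at the point of leaving usual clinical care".
- **Timing of baseline.** After describing randomisation and the care each arm receives, the same section adds: "Baseline questionnaires will also be administered at this visit". In the Table of Events, the column headed "Consent and Randomisation" stands before the column for pre-intervention data.
- **Routine items.** Under Initial / Baseline data collection: "Please note CAT, GAD, PHQ-9 FEV1 and gender are already captured routinely during clinical consultation". EQ-5D, HEIQ and the health care utilisation questionnaire are not among the items listed as routine.

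**The concern.** **Concealment.** The envelope serves a clinic, but consent is taken one patient at a time. The locked drawer protects an envelope only until it is opened. Choosing envelopes at random hides which block comes next, not the rest of a block already opened. The text describes no separately sealed slips, no independent holder, and no rule that all four patients consent first. For the second to fourth patients of a block, the envelopes may therefore not do what the plan wants of them. Someone who knows the next allocations can influence the order and timing of consent within a clinic. Selective ordering of this kind affects every between-group comparison, including the 3-month Wilcoxon comparisons (Analysis Plan, item d). It cannot be repaired in analysis, and the plan names no baseline adjustment for those tests.

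**Baseline after allocation.** If EQ-5D and health care use are reported once the arm is known, the baseline side of the cost-utility analyses (Analysis Plan, items a and b) can shift. Comparisons made only at 3 months are not touched by this second point. CAT, GAD and PHQ-9 may already exist from routine care, so they are less exposed.

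**Working it through.** The plan gives no figure for predictability, so there is none to reproduce.

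**Inputs from the plan:** fixed block of four; 1:1 allocation, so two of each arm per block; 30 to 60 per group, so 60 to 120 in total, or 60/4 = 15 to 120/4 = 30 blocks.

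**Step 1. Allocations visible before consent.** If k of the four have consented when the envelope is opened, the exposed number is (4 − k)/4 × N.

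| k | of 60 | of 120 |
|---|---|---|
| 1 | 45 | 90 |
| 2 | 30 | 60 |
| 3 | 15 | 30 |
| 4 | 0 | 0 |

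The first row is the upper case, 75% of the trial.

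**Step 2. One sealed envelope per participant, block of four still known.** There are six balanced patterns. In AABB and BBAA the last two places are fixed by what went before. In ABAB, ABBA, BAAB and BABA only the last place is. That makes 2 × 2 + 4 × 1 = 8 of 24 positions, or 33.3%: 20 of 60, or 40 of 120. The best-guess success rate is 3.5/4 = 87.5% when the whole pattern is seen at the first opening. With single envelopes it falls to (17/6)/4 = 70.8%.

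**Step 3. Varied, undisclosed block sizes.** A simulation used blocks of 2, 4 and 6 in random order with equal chance, and an observer who remembers all past allocations. About 4% of allocations were certain (about 2 of 60, or 5 of 120). Average guessability hardly moves: guessing the arm that lags behind succeeds in 75.0%, 70.8% and 68.3% of cases for blocks of 2, 4 and 6.

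**Step 4. Illustration of bias (assumed, not from the documents).** Suppose the first patient is random and the other three are ordered by prognosis, the best going to the GENIE places. The expected values of three ordered standard normal draws are +0.846, 0 and −0.846. Whichever arm the first patient enters, the GENIE mean is (0 + 0.846)/2 = 0.423 and the usual-care mean is (0 − 0.846)/2 = −0.423. The difference is 0.846 SD per fully re-ordered clinic. If this happened in 10% to 25% of clinics:

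- 0.10 × 0.846 = 0.08 SD
- 0.25 × 0.846 = 0.21 SD

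The standard error of the arm difference is √(2/30) = 0.26 SD at 30 per arm and √(2/60) = 0.18 SD at 60 per arm.

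**Step 5. Order of baseline and allocation.** The narrative describes randomisation, then care, then the questionnaires as a further task of the visit. The Table of Events runs in the same direction. No sentence places the questionnaires before the arm is revealed, and none fixes the opposite order either.

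**The case against.** The strongest reply is that a clinic may be a pre-booked group of four. Blocks of four are said to fit the clinic structure. The clinical team keeps the list of interested patients, they have at least 72 hours with the information sheet, and appointments are confirmed in advance. People, and perhaps their order, could then be settled before the envelope is opened. The enrolment and randomisation figure is not shown and might settle both the consent rule and the place of baseline. The word also, in the sentence on questionnaires, carries no time order. The pre-intervention label means that only knowledge of the arm, not treatment, could affect baseline, and past visits and hospital nights are less open to that than opinions are.

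Part of this stands. The exposure may be as low as zero, the order of baseline is an inference, and the documents do not allow the size of any bias to be estimated. The illustration in Step 4 needs perfect ranking, freedom to re-order and one consistent direction. Even so, it stays below one standard error at 30 per arm, and exceeds it at 60 per arm only near the top of the assumed range. The shared spreadsheet yields an envelope number and is not said to show the sequence.

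The main point is not removed. The whole-pattern envelope is explicit in the text. An interested patient with an appointment has not yet consented, and the text has no rule that all four consent first. The utilisation form itself accepts a best guess, so its answers are not immune to knowledge of the arm.

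**Conclusion.** The concern holds. A team following the text as written can see up to three of every four allocations before those patients consent: up to 45 of 60 or 90 of 120. This upper figure assumes complete blocks, no inner sealing and one consented patient at opening. It falls to 0 if all four consent first. This undercuts the plan's own stated reason for using envelopes.

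The second part holds at the strength of a suggestion: two places point to randomisation before the baseline questionnaires, and nothing in the text says otherwise. It matters mainly for EQ-5D and health care use, which feed the cost-utility analyses listed under Primary Outcomes.

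The 0.08 to 0.21 SD range shows what modest re-ordering could do under the stated assumptions. It is not a forecast.

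**What to change.** 1. Have a colleague who neither recruits nor delivers GENIE prepare one allocation list in advance, running across clinics. Balance is still kept within each completed block.
2. Use one sealed, opaque, sequentially numbered envelope per participant.
3. Open it only after that participant has signed consent and completed the baseline questionnaires.
4. Place randomisation after baseline data collection in Selection and patient information and in the Table of Events, and state the order outright.
5. Optionally, vary the block size and do not disclose it. This cuts the share known with certainty from 33% to about 4%, but barely changes average guessability. The reference cited for blocking is, by its title, about randomly selected block sizes, whereas the plan fixes the block at four.

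**Cost.** 60 to 120 small envelopes in place of 15 to 30 (taking one per block now; the plan gives no count), a one-off list, and re-ordered tasks within the same visit. There is no extra visit and no change to the sample size.

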Participation in the study will be offered to every patient in pulmonary rehabilitation or maintenance exercise programs in the east of Southampton. Participants must also fulfill the inclusion criteria. Patients already referred into pulmonary rehabilitation groups will be approached and asked if they wish to participate in the study at assessment and at the end of pulmonary rehabilitation in their post PR review appointment. The appointments are offered to patients after completion of the patients PR program, usually after 12 sessions by the clinical team. Therefore, it is envisaged that a minimum of 30 patients per arm will be recruited; these include PR leavers, maintenance reviews referrals. Appointments will be offered in person, via the telephone with confirmation letter or text. The numbers from each of these groups cannot be predicted as it is dependent on clinical opinion, however the aim to have a minimum of 30 participants, with the aim to recruit up to 60 to ensure meaningful analysis.

Inclusion criteria;

- adults between 18 and 95 with a predominant diagnosis of COPD
- Ability to understand spoken English
- Enrolled in PR or maintenance therapy
- Ability and capacity to make their own decision and consent freely

Exclusion Criteria;

- No clear COPD diagnosis
- Inability to consent

The Intervention

This evaluation aims to demonstrate the effectiveness and increase social interactions and community networks in the COPD population in Southampton city.

Rational for GENIE is connecting people to new resources

The aim of using GENIE is to connect people with long-term conditions to local and (in the future) online resources to support them in their everyday lives. Objectives of GENIE:

- Raise awareness of the links and functions that social networks enable (for individuals and local community groups and organisations).
- Use social networks to engage patients in reflecting on their needs and support, support access to further resources and knowledge and introduce practices related to lifestyle, illness management, and behaviour change.
- Strengthen existing individual and community networks and improve patient engagement.

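### One block-of-four envelope per clinic guarantees equal arms only if every clinic fills its blocks, and the text gives no rule for unused places

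*Combined protocol and SAP*

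**What the plan says.** The randomisation method is described in the block randomisation paragraphs under Implementation Design, which justify blocking by the small sample.

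- Block size: "The intention is to randomize in blocks of four, as this will complement the clinic structure".
- Contents of an envelope: "each envelope will contain a pre-determined allocation pattern for that clinic (AABB, ABAB, BABA etc", and so on.
- Choice of envelope, from a spreadsheet of random numbers: "The next sequential number will be selected, which will then correspond to an envelope with the predetermined sequence".
- Property claimed: "sequence in the envelopes is also random, but ensures 50/50 grouping of participants".
- Target: "recruitment needs to reach at least 30 patients, in each group, however the maximum could be 60 in each group, 120 patients in total". Then: "Therefore recruitment could take between 6-9 months", and the period may be extended.

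The preceding text on selection and patient information adds that there is one venue, that people consent and are randomised at the point of leaving usual care, and that they may opt out at that point. The Population section says of the referral sources: "The numbers from each of these groups cannot be predicted as it is dependent on clinical opinion".

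The text does not state how often clinics run, how many people attend one, what happens to unused places in an envelope, or how a fifth person at a clinic is allocated.

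**The concern.** A permuted block of four is balanced when it is complete, not before. The plan ties each block to one clinic and draws another envelope by number. Read naturally, a clinic that randomises one, two or three people uses part of an envelope, and the next clinic opens a new one. The equal split then no longer follows from the procedure. Blocking was chosen because the trial is small; each discarded remainder moves the scheme towards simple randomisation, which is what blocking was meant to avoid.

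An envelope that holds a whole clinic's pattern also shows the remaining allocations to whoever opens it. The same change removes that weakness.

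**Working it through.** **1. The plan's own figure.** There are six balanced patterns of four. 60/4 = 15 and 120/4 = 30 whole blocks, so 30:30 and 60:60 are reproduced exactly, provided every block is filled.

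**2. A block cut short.** Let d be the arm difference after k people, counted over the six patterns.

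| k | Chance of imbalance | Mean of d² |
|---|---|---|
| 1 | 1 (always off by 1) | 1 |
| 2 | 1/3 (off by 2) | 4/3 |
| 3 | 1 (always off by 1) | 1 |
| 4 | 0 | 0 |

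**3. How often a clinic falls short.** The weekly rate follows from the plan: 60 in 9 months (39 weeks) is 1.5; 60 in 6 months (26 weeks) is 2.3; 120 in 9 months is 3.1; 120 in 6 months is 4.6. Turning this into people per clinic needs a clinic frequency, which is an assumption. With Poisson counts, the chance of fewer than four at a clinic is:

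| Assumed frequency | 60 in 9 mo | 60 in 6 mo | 120 in 9 mo | 120 in 6 mo |
|---|---|---|---|---|
| Twice weekly | 99% | 97% | 93% | 80% |
| Weekly | 93% | 80% | 63% | 32% |
| Fortnightly | 63% | 32% | 14% | 2% |
| Monthly | 10% | 1% | 0.1% | <0.1% |

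These include clinics at which nobody is randomised. Among weekly clinics with at least one person, the range is 32% to 91%.

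Alternatively, suppose each clinic has four booked places (assumed). The chance that fewer than four are randomised is 1 − q⁴, where q is the proportion who attend and consent: 34% at q = 0.9, 59% at 0.8, 76% at 0.7.

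**4. Effect on the arms if remainders are discarded, 60 recruits.** SD of the final difference = √(number of clinics × mean of d²). The SD of one arm's size is half of that.

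- Two per clinic: √(30 × 4/3) = 6.3, so 3.16 for one arm. 30 ± 1.96 × 3.16 gives 24 to 36. An exact 30:30 split has probability 13%; the smaller arm is 26 or fewer with probability 27%.
- One to four per clinic, equally likely: mean of d² = (1 + 4/3 + 1 + 0)/4 = 0.833 over 60/2.5 = 24 clinics; √(24 × 0.833) = 4.5, giving about 26 to 34.
- Three per clinic: √20 = 4.5; exact split 18%.
- One per clinic: √60 = 7.7, the same as simple randomisation.

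**5. Larger clinics.** With monthly clinics, fewer than four is uncommon, but a count that is not a multiple of four still leaves the last block short, at about 75% of clinics. There are only 6 to 9 such clinics, so the SD of the difference is about √(6 × 0.833) = 2.2 to √(9 × 0.833) = 2.7.

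**6. Cost in precision and recruits.** Relative efficiency = 4ab/N². At 33:27 it is 4 × 33 × 27/3600 = 0.99; at 36:24 it is 4 × 36 × 24/3600 = 0.96. Simulating recruitment until both arms reach 30, with remainders discarded, gives a median total of 64 at two per clinic (95th percentile 73), 63 at one to four per clinic (69) and 65 at one per clinic (77).

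**7. With carry-over.** In one continuous sequence of blocks of four, the difference never exceeds 2 and is 0 at 60 and at 120.

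**The case against.** The best defence is that the block size was chosen to fit the clinic structure. That is the only indication of clinic size in the text, and it points to about four. Interested patients' names are held on a list and appointments are arranged with them, so booking in fours is possible. This stands as evidence of intent. It does not secure the claim, because people may still opt out at the visit after four have been booked.

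Second, no sentence says that unused places are thrown away. The wording for the envelope and the fresh draw suggest it, but carry-over would be compatible with the text and would keep the arms within two. The section headed Identification, enrolment and randomisation is a figure not available here, so a rule may be given there. This stands, and the imbalance figures are conditional on discarding.

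Three stronger readings are tempting, and the documents do not support them.

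- That the planned recruitment rate makes short blocks likely. The plan gives people per month, not per clinic; step 3 runs from under 0.1% to 99% according to the assumed clinic frequency.
- That the minimum of 30 per group cannot be met. At a total of exactly 60, any split other than 30:30 leaves one arm below 30, but 60 is not a stopping total: up to 120 may be recruited and the period can be extended.
- That the lack of balancing between pulmonary rehabilitation leavers and maintenance patients shows a block fault. With an assumed 50% mix and 30 per arm, a chance difference of 1.96 × √(0.25 × 2/30) = 0.25, or 25 percentage points, is what unstratified allocation allows even when every block is filled.

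**Conclusion.** The point holds in limited form. The claim "but ensures 50/50 grouping of participants" does not follow from clinic-level blocks of four unless every clinic randomises four people or a whole multiple of four, and the text has no rule for the other cases. The departure matters only if remainders are discarded, which the wording suggests but does not state, and its size depends on unstated clinic frequency and numbers. Under the small-clinic assumptions of step 4, an arm could be about 24 to 36 out of 60, or 26 to 34 with more varied clinics. The consequence is modest: allocation remains random, no bias is shown, at most about 4% of efficiency is lost at 24:36, and typically three to five more recruits would bring both groups to 30. It merits correction because a stated design property is not delivered and the remedy is simple.

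**What to change.** - Replace the clinic-level envelopes with one pre-generated, continuous blocked sequence in sealed, opaque, consecutively numbered envelopes, one allocation in each.
- State that each participant takes the next envelope whatever the clinic, so unused places carry over. This also settles what happens to a fifth person.
- Replace the claim of an assured equal split with a statement that the arms are kept within two of each other.
- State the expected clinic frequency and number per clinic.

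Optionally, keep one sequence for pulmonary rehabilitation leavers and one for maintenance reviews. The overall difference is then at most 2 + 2 = 4. This is a separate improvement and is not needed to repair the blocks.

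The cost is re-packing the envelopes and a few sentences in the protocol. Sample size, visits and analysis are unchanged.
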